5.4.2 Exclusion Criteria

- Subject has a current diagnosis of a coagulation disorder, bleeding diathesis, progressive peripheral vascular disease, post-herpetic neuralgia or uncontrolled diabetes mellitus;
- Subject is currently participating in a clinical investigation that includes an active treatment arm;
- Subject has been implanted with or participated in a trial period for a neurostimulation system;
- Subject has an infusion pump;
- Subject has evidence of an active disruptive psychological or psychiatric disorder as determined as per standard of care;
- Subject has a current diagnosis of a progressive neurological disease as determined by the Investigator;
- Subject is immunocompromised;
- Subject has an existing medical condition that is likely to require repetitive MRI evaluation in the future (i.e. epilepsy, stroke, multiple sclerosis, acoustic neuroma, tumor);
- Subject has history of cancer requiring active treatment in the last 12 months;
- Subject has an existing medical condition that is likely to require the use of diathermy in the future;
- Subject has documented history of allergic response to titanium or silicone;
- Subject has a documented history of substance abuse (narcotics, alcohol, etc.) or substance dependency in the 6 months prior to baseline data collection;
- Subject is a female candidates of child bearing potential that are pregnant (confirmed by positive urine/blood pregnancy test);

- Subject has life expectancy of less than 6 months;
- Subject is involved in an injury claim under current litigation

6 Procedures

The clinical study will be conducted in accordance with the CIP. All parties participating in the conduct of the clinical study will be qualified by education, training, or experience to perform their tasks and this training will be documented appropriately. Approval from the Sponsor must be received prior to initiating study procedures.

Patients will be informed about the study to determine if he/she is interested in participating. Eligible patients will read, sign and date the informed consent and will continue to participate in the study as subjects. Subjects diagnosed with chronic intractable back and/or leg pain, with no prior history of SCS therapy, will be considered for inclusion in this study and will be assessed at baseline and all follow up visits.

The assessments will include:

- Pain intensity as assessed by the Visual Analog Scale (VAS)
- Quality of life as assessed by the European Quality of Life 5 Dimensions (EQ-5D)
- Disability as assessed by the Oswestry Disability Index (ODI)
- Anxiety and Depression as assessed by the Hospital Anxiety and Depression Scale (HADS)
- Pain Catastrophizing as assessed by the Pain Catastrophizing Scale (PCS)
- Satisfaction as assessed by the Patient Global Impression of Change (PGIC)
- Medication Usage
- Adverse Events

After baseline evaluation, subjects will undergo a SCS trial using the Abbott Invisible Trial system. During the trial implant phase, SCS leads will be implanted in the dorsal column based on physician discretion. According to standard clinical practices performed in the United States (US), the trial phase will last around 3-7 days. At the start of the trial phase, patients will be programmed with the first ON/OFF stimulation pattern (30 second STIM ON, 90 seconds STIM OFF). Patients who do not achieve adequate pain relief (at least 50% reduction in back and/or leg VAS from baseline) within the first 3-4 days will be reprogrammed to a new ON/OFF stimulation pattern (5 seconds ON/ 15 seconds OFF). Patients, who still do not achieve adequate pain relief within 2 to 3 days from reprogramming, will be reprogrammed to a continuous mode of BurstDR[™] stimulation and their trial evaluation will continue. These patients will be evaluated for an additional 2 days. At the end of the SCS trial, all subjects that experience at least 50% pain relief (according to average back and/or leg VAS) using one of the two microdosing burst stimulation paradigms will be considered further participation in the study. See Figure 1.

Patients who have passed the trial phase and have received permanent implantation will be programmed based on the stimulation mode used for their trial success. Pain intensity, quality of life, disability, anxiety, depression, pain catastrophizing, satisfaction, and medication usage will be assessed at baseline, after SCS trial and at the 1, 3 and 6 month follow up. Adverse events will be collected throughout the study period.

During the month leading to the 1 month follow up visit, patients' pain relief will be evaluated on a weekly basis according to Figure 2. Briefly, patients who do not achieve adequate pain relief (greater or equal to pain relief achieved during the trial phase) will try lower stimulation ON/OFF ratios to determine the lowest possible stimulation ratio whilst maintaining adequate pain relief. This stimulation ON/OFF ratios will start from a ratio of 1:12 (Program 1) and increase to a potential ON/OFF ratio of 1:3 (Program 5) – Once the most optimal microdosing program is determined (as per algorithm in Figure 2), the patient will continue

the rest of the study with that program. If inadequate pain relief is experienced anytime during the study, the BurstDRTM microdosing parameters will be altered as per the algorithm in Figure 2.

The following sections provide a detailed description of procedures required by this CIP.

6.1 Informed Consent Process

The Principal Investigator or his/her authorized designee will conduct the Informed Consent Process, as required by applicable regulations and the center's IRB/EC. This process will include a verbal discussion with the subject on all aspects of the clinical investigation that are relevant to the subject's decision to participate, such as details of clinical investigation procedures, anticipated benefits, and potential risks of clinical investigation. During the discussion, the Principal Investigator or his/her authorized designee will avoid any improper influence on the subject and will respect subject's legal rights. The subject shall be provided with the informed consent form written in a language that is understandable to the subject and has been approved by the center's IRB/EC. The subject shall have adequate time to review, ask questions and consider participation.

If the subject agrees to participate, the Informed Consent form must be signed and dated by the subject and by the person obtaining the consent. The signed original will be filed in the subject's hospital or research charts, and a copy will be provided to the subject.

The Principal Investigator or his/her authorized designee will document the informed consent process in the subject's hospital and/or research charts. The date of signature will be entered on an applicable Case Report Form (CRF).

Failure to obtain informed consent from a subject prior to clinical investigation enrollment should be reported to Sponsor within 5 working days and to the reviewing center's IRB/EC according to the IRB's/ EC's reporting requirements.

If, during the clinical investigation, new information becomes available that can significantly affect a subject's future health and medical care, the Principal Investigator or his/her authorized designee will provide this information to the subject. If relevant, the subject will be asked to confirm their continuing informed consent in writing.

6.2 Screening

Potential patients presenting at the investigational sites will be fully informed about the clinical investigation, following the established Informed Consent process (described in section 6.1). Once a duly dated and signed Informed Consent Form is obtained, the screening procedures may begin.

Records of patients who are screened must be maintained.

In case the subject does not meet all inclusion criteria or meets any of the exclusion criteria, the subject is considered a screening failure. The Principal Investigator or the delegated study personnel will record the screening failure in the hospital records and on a screening log as required.

6.3 Point of Enrollment

Subject is considered enrolled in the clinical investigation from the moment the subject has provided a written Informed Consent and has been confirmed to meet all inclusion criteria and none of the exclusion criteria.

The Principal Investigator or delegated study personnel will record enrollment information (name of the clinical investigation, date of consent and Inclusion/exclusion information) in the hospital records and complete and submit an applicable CRF in a timely manner.

Notification of enrollment to the Sponsor is considered to have occurred when the Sponsor has received the applicable CRF.

6.4 Scheduled Procedures

The Principal Investigator is responsible for ensuring all clinical investigation data is collected as required per CIP scheduled procedures.

6.4.1 Baseline

Baseline visit activities can occur at the same visit of enrollment after the informed consent has been obtained.

The following assessments and information will be collected at the baseline visit

- Demographics- include subject's Age and Gender
- Physical examination- include subject's height and weight
- Indication for device/ procedure
- Previous therapies tried for indications
- Clinical investigation specific examinations
 - Pain intensity as assessed by the VAS
 - Quality of life as assessed by the EQ5D
 - Disability as assessed by the ODI
 - Anxiety and Depression as assessed by the HADS
 - Pain Catastrophizing as assessed by the PCS
 - Medication Usage

Timing of visit	Activities at visit	Case Report Form
Screening/Baseline	 Subject assesses pre-trial pain levels, quality of life, disability, anxiety, depression, pain catastrophizing, and medication usage. 	 VAS Form EQ-5D Form ODI Form HADS Form PCS Form Medication Usage Form

6.4.2 SCS Trial

During the trial implant phase, SCS leads will be implanted in the dorsal column based on physician discretion. According to standard clinical practices performed in the United States (US), the trial phase will last around 3-7 days. At the start of the trial phase, patients will be programmed with the first ON/OFF stimulation pattern (30 second STIM ON, 90 seconds STIM OFF). Patients who do not achieve adequate pain relief (at least 50% reduction in back and/or leg VAS from baseline) within the first 3-4 days will be reprogrammed to a new ON/OFF stimulation pattern (5 seconds ON/ 15 seconds OFF). Patients, who still do not achieve adequate pain relief within 2 to 3 days from reprogramming, will be reprogrammed to a continuous mode of BurstDR[™] stimulation and their trial evaluation will continue. These patients will be evaluated for an additional 2 days. At the end of the SCS trial, all subjects that experience at least 50% pain relief (according to average back and/or leg VAS) using one of the two microdosing burst stimulation paradigms will be considered further participation in the study. Patients who still do not achieve adequate

pain relief will be reprogrammed to a continuous mode of BurstDRTM stimulation and their trial evaluation will continue. These patients will be evaluated for an additional 2 days.

The following assessments and information will be collected at the SCS Trial visit

- Surgery Form
- Clinical investigation specific examinations
 - Programming Form

The following activities will be performed at the SCS Trial visit:

- SCS Trial Lead(s) Implant
- EPG Device programming

Timing of visit	Activities at visit	Case Report Form	
SCS Trial	SCS trial lead implant	Surgery Form	
	EPG programming	Programming Form	

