5.3.1 Primary Endpoint

• Evaluate the change in pain intensity between baseline, trial and long-term follow up evaluations using the Visual Analog Scale (VAS) assessments.

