5.4.1 Inclusion Criteria

- Subject is able to provide informed consent to participate in the study;
- Subject diagnosed with chronic intractable pain associated with back and/or limbs;
- Subject is 18 years of age or older;
- Subject has failed to respond to at least 6 months of conventional treatment which may include pharmacological treatment, physical therapy, epidural injections;
- Subject has a back and/or leg pain intensity of at least 6.0 cm out of 10.0 cm on the average back and/or leg pain VAS at baseline;
- Subject's medical record has been evaluated by the Investigator to ensure that the subject is a
 good candidate for a neurostimulation system;
- Subject is on stable pain medications with a total opioid for at least 28 days prior to enrolling in this study, and is willing to stay on those medications with no dose increase until the 3 month visit;
- Subject is willing to cooperate with the study requirements including compliance with the regimen and completion of all office visits;
- Female candidates of child-bearing potential agree to commit to the use of an effective method of contraception (including but not limited to sterilization, barrier devices, oral contraceptives, intrauterine devices (IUDs), condoms, rhythm method, or abstinence) for the duration of the study

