6.4.3 End of Trial

During the End of Trial visit, subjects will complete the same questionnaires completed during the baseline visit. If the VAS score is < 50% of the VAS collected during the screening visit and is not using the two microdosing burst stimulation paradigms, the subject will exit the study. Subjects whose VAS score at the end of the trial is >50% of the VAS collected during the screening visit and is using one of the two microdosing burst stimulation paradigms, will be considered for permanent lead and IPG implantation.

The following assessments and information will be collected at the End of Trial visit:

- Clinical investigation specific examinations
 - Pain level as assessed by the VAS
 - Quality of life as assessed by the EQ-5D
 - Disability as assessed by the ODI
 - Anxiety and Depression as assessed by the HADS
 - Pain Catastrophizing as assessed by the PCS
 - Satisfaction as assessed by the PGIC
 - Medication usage;
 - Programming Form

Timing of visit	Activities at visit	Case Report Form
End of Trial	 Subject assess pain levels, quality of life, disability, anxiety, depression, pain catastrophizing, satisfaction, medication usage, and programming 	 VAS Form EQ-5D Form ODI Form HADS Form PCS Form PGIC Form Medication Usage Form Programming Form

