7.1.1 Primary [Safety/Effectiveness] Endpoint Hypothesis(es)

7.1.1.1 Analysis Methodology

The primary analysis to assess improvement in pain intensity, using VAS, will be conducted using repeated measures ANOVA (RMANOVA). Post-hoc Tukey's pairwise comparisons will follow to determine specific differences between follow-up visits. Secondary analyses to assess improvements in quality of life, disability, anxiety, depression catastrophizing and satisfaction will be conducted using repeated measures ANOVA (RMANOVA) or the most appropriate statistical methods.

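### Entry and the 50% trial-relief rule rest on an undefined back/leg VAS with no index site, and the primary VAS endpoint names no site, so the analysed variable is not fixed

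*Combined protocol and SAP*

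**What the plan says.** **Entry** (sections 1.6.1 and 5.4.1): the subject must score "at least 6.0 cm out of 10.0 cm on the average back and/or leg pain VAS at baseline". The site that qualifies the subject is not recorded as an index site.

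**Relief during the SCS trial** (1.3, 5.1, the introduction to 6, and 6.4.2, all worded alike): the reprogramming trigger is failure to reach "at least 50% reduction in back and/or leg VAS from baseline". The end-of-trial condition for continuing is "at least 50% pain relief (according to average back and/or leg VAS". The word average appears in the second and not in the first, and is defined in neither.

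**End of Trial** (6.4.3): the gate is restated on one unspecified score. The exit sentence begins "If the VAS score is < 50% of the VAS collected during the screening visit", and the sentence on permanent implant begins "Subjects whose VAS score at the end of the trial is >50% of the VAS collected during the screening visit".

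**Primary endpoint** (1.4.1 and 5.3.1): "Evaluate the change in pain intensity between baseline, trial and long-term follow up evaluations using the Visual Analog Scale (VAS) assessments". Section 7.1.1.1 applies repeated measures ANOVA to VAS. Neither names back, leg or a combination. The baseline list in 6.4.1 has one line, "Pain intensity as assessed by the VAS", with no separate back and leg items.

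**Context**: there is no responder endpoint. Section 7.6 says there are no formal success criteria, and 7.1 that formal hypothesis testing is not required. Section 7.3 nevertheless sets a type-1 error rate of 0.05 for all tests, and 7.1.1.3 rules out imputation.

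**The concern.** Two decisions and one outcome depend on a VAS that the plan does not pin down.

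The first decision is entry and the second is passing the SCS trial. If either site may count for each, the two need not refer to the same pain. A subject with back 8 cm and leg 2 cm enters on the back. If the leg falls to 1 cm and the back stays at 8 cm, the leg has fallen by 50% and the rule is met, although the qualifying pain has not changed. The gate decides who receives a permanent implant and so who can contribute VAS data at 1, 3 and 6 months. It also carries forward, because adequate relief after implant is judged against the relief achieved in the trial phase.

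The outcome is the primary VAS itself. From the plan text an analyst cannot tell whether the dependent variable is back, leg, their mean, or a site that differs between subjects. In an open-label study that choice could be made after the data have been seen. Section 7.1 says the results may inform a later level-1 study, so what was measured needs to be clear.

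**Working it through.** The plan gives no responder rate, VAS standard deviation, baseline mean or between-site correlation, so it has no figure to reproduce. Only the 6.0 cm threshold and the 50% rule come from the protocol. All other inputs below are assumptions.

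**Check 1: chance passes with no true effect.** Let a site have true level L, with independent normal reading error of SD s at baseline and at end of trial. It passes if the second reading is at most half the first. The difference (second reading minus half the first) has mean 0.5L and variance s² + 0.25s² = 1.25s², so

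P(pass) = Φ(−0.5L / (s√1.25)).

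| True level L | s = 1.0 | s = 1.5 |
|---|---|---|
| 8 cm | Φ(−3.58) = 0.02% | Φ(−2.39) = 0.85% |
| 7 cm | Φ(−3.13) = 0.09% | Φ(−2.09) = 1.8% |
| 6 cm | Φ(−2.68) = 0.4% | Φ(−1.79) = 3.7% |
| 2 cm | Φ(−0.89) = 18.6% | Φ(−0.60) = 27.5% |

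The either-site rate is p_back + p_leg − p_back × p_leg. For back 8, leg 2:
- s = 1.0: 0.0002 + 0.186 − 0.00004 = 18.6%
- s = 1.5: 0.0085 + 0.275 − 0.0023 = 28.1%

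Simulating the same model, with scores limited to 0–10 and a baseline back reading of at least 6 required, gives:

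| Case, no true effect | Pass rate, s = 1.0 to 1.5 |
|---|---|
| Back 8, leg 2: either site | about 18–28% |
| Back 8, leg 2: qualifying site only | 0 to under 1% |
| Back 8, leg 6: either site | 0.4 to about 4.4% |
| Back 8, leg 7: either site | 0.1 to 2.5% |
| Back 8, leg 2: mean of the two sites | 0 to 1.2% |

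The driver is the mild second site: from 2 cm, a 1 cm fall is enough.

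**Check 2: a real effect at both sites.** Assume baselines of 7.5 cm (qualifying) and 4.0 cm, a true 40% reduction at each, SD 2.0 cm and between-site correlation 0.5.
- Qualifying site: the mean falls to 4.5 and the threshold is 3.75, so Φ(−0.75/2.0) = 35%.
- Other site: the mean falls to 2.4 and the threshold is 2.0, so Φ(−0.4/2.0) = 42%.
- Both sites, by simulation: 23%.
- Either site: 35 + 42 − 23, which is 55% before rounding the terms.
- Mean of the two sites, by simulation: 37%.

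About 55 − 35 = 20% pass only on the non-qualifying site. If all 60 subjects had this profile, that would be about 12 (0.20 × 60).

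**Check 3: sections 6.4.2 and 6.4.3 side by side.** Take a baseline of 8.0 cm. Relief of at least 50% under 6.4.2 means a score of 4.0 cm or less. Read literally, the implant sentence in 6.4.3 applies to scores above 50% of screening, that is above 4.0 cm. The two sections point in opposite directions, and 6.4.3 names no site.

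**The case against.** **Average may mean the two-site mean.** Entry and the end-of-trial condition both contain that word. On this reading back 8, leg 2 has mean 5.0, below the entry threshold, and a move to 8 and 1 is a fall from 5.0 to 4.5, or 10%. The cross-site pass then almost disappears. This stands: the problem is conditional on the either-site reading. But the reprogramming trigger omits the word, and average may equally mean average pain intensity over time. The plan does not choose.

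**The back 8, leg 2 case is favourable to the criticism.** It is. With a second site at 6 to 7 cm the gap is small, and the documents do not show how many subjects have a mild second site.

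**A reader might infer an inflated responder rate or an upward-biased primary result.** The documents do not support this. No responder rate is an endpoint, and the 50% rule only governs continuation. If VAS were analysed at the treated site, subjects who passed only on the other site would show little change and would dilute the result. A gate on the analysed site would select more strongly on chance falls in it. The direction of any bias is not established.

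**A reader might infer that the primary endpoint uses the same either-or wording, or that the better site will be picked.** It does not use that wording: it names no site. Nothing in the text says the better site would be chosen; the text only fails to rule it out.

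**The VAS form or a separate SAP may settle this.** Appendix D keeps the case report forms under separate cover, and section 7 allows for a separate SAP. Either may help, but the primary variable should be readable from the endpoint and analysis sections.

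**Conclusion.** The point holds as a defect of definition with practical consequences. Entry and trial relief rest on an undefined back/leg VAS with no index site, and the primary endpoint and its analysis name no site.

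The undefined primary variable is clear from the text and needs no assumption. The size of the cross-site pass does: it requires the either-site reading, pain scored at both sites and a mild second site. Under those conditions it is material, about 18 to 28% against under 1% with no true effect. It falls to about 0.1 to 4.4% with a second site at 6 to 7 cm, and to 0 to 1.2% under the two-site mean. Two plausible readings of one phrase can therefore differ by more than tenfold, which is why the text should choose. None of this shows that the primary result would be inflated.

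Importance is moderate: the study is a feasibility trial without success criteria, but it tests at 0.05 and may inform a later trial.

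**What to change.** **Analysis.** In 5.3.1 and 7.1.1.1, define one primary VAS variable: the score at the site that met 6.0 cm at baseline, or the higher of the two if both did. Fix it per subject before the SCS trial and use it at every visit in the repeated measures ANOVA. Report the other site as secondary, and derive any reported 50% relief rate on the index site. Such a site exists even if entry was meant on the two-site mean, because a mean of at least 6.0 cm implies that the higher site is at least 6.0 cm.

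**Continuation gate.** No rule is proposed here. Define what average back/leg VAS means, and reconcile 6.4.2 (at least 50% relief) with 6.4.3, which names no site and continues subjects whose score exceeds 50% of the screening score. Make the matching text in 1.3, 5.1 and the introduction to 6 agree.

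**Cost.** Wording only, with no new data, if the VAS form already scores back and leg separately; otherwise the form must do so from baseline. A reported relief rate may be slightly lower on the index site than under an either-site count.

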6.7 Study Flow Chart

The Study Flow Chart and the Table 2 below summarize subject flow and requirements of this clinical investigation.

Figure 1: Study Flow Chart

Visit	Enrollment	Baseline	SCS Trial	End of Trial	SCS Implant	Activation	Follow-up Visits*
Study Activity							
Informed Consent Process	х						
Inclusion/Exclusion Criteria Screening	х						
VAS Assessment		X		Х			Х
Enrollment Form	Х						
EQ-5D Assessment		X		X			Х
ODI Assessment		X		Х			Х
HADS Assessment		X		X			Х
PCS Assessment		X		X			Х
PGIC Assessment				X			Х
Trial System Implant			х				
Permanent System Implant					x	x	
Adverse Event	(X)	(X)	(X)	(X)	(X)	(X)	(X)
Deviation	(X)	(X)	(X)	(X)	(X)	(X)	(X)
Termination	(X)	(X)	(X)	(X)	(X)	(X)	(X)
Death	(X)	(X)	(X)	(X)	(X)	(X)	(X)

Table 2: List of all clinical investigation specific tests and procedures

(X) If applicable

* Follow up visit assessments will be performed at months $1(30 \pm 21 \text{ days})$, $3(90 \pm 21 \text{ days})$ and $(180 \pm 21 \text{ days})$

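### The plan does not say how the primary baseline-to-trial VAS change treats subjects switched to continuous BurstDR, or who enters it, and no scheduled form holds their microdosing VAS

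*Combined protocol and SAP*

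**What the plan says.** The primary objective (5.2.1) is the efficacy of microdosing in patients new to neuromodulation. The primary endpoint (5.3.1) is VAS change across baseline, trial and long-term follow-up. Sections 1.8 and 6.4.3 place the trial measurement at the End of Trial visit: "During the End of Trial visit, subjects will complete the same questionnaires completed during the baseline visit".

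In 6.4.2 subjects start on one microdosing pattern. Those without adequate relief in 3-4 days move to a second. Then: "Patients, who still do not achieve adequate pain relief within 2 to 3 days from reprogramming, will be reprogrammed to a continuous mode", with 2 further days of evaluation. The group that may continue is "all subjects that experience at least 50% pain relief (according to average back and/or leg VAS") on one of the two microdosing patterns. The same section repeats the continuous-mode step after that sentence, and it says that "the trial phase will last around 3-7 days".

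Section 6.4.3 provides for a subject whose VAS is below 50% of the screening value and who "is not using the two microdosing burst stimulation paradigms, the subject will exit the study". Those considered for implant are "Subjects whose VAS score at the end of the trial is >50% of the VAS collected during the screening visit" and who are on a microdosing pattern.

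The SCS Trial visit lists only the Surgery and Programming Forms. In 6.7, "Table 2: List of all clinical investigation specific tests and procedures" marks VAS at Baseline, End of Trial and follow-up only.

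Section 7.1.1.1 specifies repeated measures ANOVA with Tukey comparisons, and 7.1.1.3 rules out imputation. Section 7 defines no analysis set. The separate SAP is optional, and analysis sets are not among the topics listed for it.

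**The concern.** Subjects who fail both microdosing patterns carry the least favourable information about microdosing. The plan does not say how their trial VAS counts, and the score that would represent them may not reach the database. Whether they enter the baseline-to-trial contrast depends on the very change being measured.

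Two outcomes are possible. Leaving these subjects out gives a change among people chosen for having a large change. Keeping them with the score on file gives an average over two stimulation modes. The primary objective asks for neither.

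Section 7.1 says that the results may be used to generate a later study with formal hypothesis testing, so an inflated trial-phase change could enter its assumptions. Analysts can choose an analysis set later, but they cannot supply a microdosing VAS that was never captured.

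**Working it through.** The plan has no figure to reproduce: 7.1.1.2 says that no sample size calculation is required.

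**1. VAS against programming steps**

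| Point in trial phase | Mode just evaluated | VAS needed? | Scheduled form with VAS |
|---|---|---|---|
| Day 3-4 | First microdosing pattern | Yes, for the 50% relief check | None |
| 2-3 days later | Second microdosing pattern | Yes, same check | None |
| End of Trial, subject passed | Microdosing | Yes | VAS Form |
| End of Trial, subject failed both | Continuous (better-supported reading) | Yes | VAS Form |

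The last row rests on 6.4.3, which expects some subjects not to be on microdosing at that visit.

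**2. Timing.** Switch to continuous mode: 3 + 2 = 5 to 4 + 3 = 7 days. End of evaluation: 5 + 2 = 7 to 7 + 2 = 9 days. The stated length is around 3-7 days.

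**3. Two ways to run the model.** Subjects who fail both patterns do not go on to implant (1.8, 6.4.2), so they have no 1, 3 or 6 month VAS.
- Complete rows: every double failure is dropped, and the baseline-to-trial change covers only subjects selected on at least 50% relief.
- All available data: double failures stay in, with a continuous-mode score.

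**4. Size of the responders-only excess (all inputs assumed).** Let f be the share failing both patterns, R the mean reduction in responders and F that in failures.

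All-trialed mean = (1 - f)R + fF, so excess = R - all-trialed mean = f(R - F).

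One-site model, 1,000,000 simulated subjects: baseline normal (mean 7.5, SD 1), truncated to 6-10 cm; percent relief normal, capped at 100, with its mean set so that a share f falls below 50%.

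| SD of relief (points) | f | All trialed (cm) | Responders only (cm) | Excess (cm) |
|---|---|---|---|---|
| 20 | 10% | 5.68 | 5.97 | 0.29 |
| 20 | 20% | 5.06 | 5.59 | 0.53 |
| 20 | 40% | 4.19 | 5.17 | 0.98 |
| 30 | 10% | 6.21 | 6.59 | 0.39 |
| 30 | 20% | 5.47 | 6.21 | 0.74 |
| 30 | 40% | 4.31 | 5.73 | 1.42 |

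Differences are taken before rounding. Check on the last row: F = (4.31 - 0.6 x 5.73)/0.4 = 2.18, and 0.4 x (5.73 - 2.18) = 1.42.

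Two-site model: back and leg baselines mean 6.5, SD 1.8, correlation 0.3, clipped to 0.5-10 cm, kept if either is at least 6.0; relief correlation 0.5 or 0.8; a responder has at least 50% relief on either site; change is measured on the site with the higher baseline. Over SD 20-30 points the excess is 0.25-0.39 cm at f = 10%, 0.45-0.73 cm at 20% and 0.83-1.38 cm at 40%.

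Both models draw one relief value per site and set f directly; they do not model the two patterns in sequence.

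**5. Mixed-mode shift.** Shift = f x d, where d is the extra reduction on continuous mode. The Synopsis reports earlier results in which microdosing did not change efficacy; on that premise d = 0 and the shift is 0. With d = 1-2 cm: 0.2 x 1 = 0.2 cm up to 0.4 x 2 = 0.8 cm.

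**The case against.** The strongest reply is that little is at stake and much is inferred. The study has no formal hypotheses (7.1) and no success criteria (7.6). Going on only with trial responders is openly stated (1.8). Missing data will be reported by visit and outcome, so the loss of failures will be visible. The End of Trial Programming Form shows the mode, so a responder proportion can be derived and continuous-mode scores can be separated. All of this stands, and it limits the point to the baseline-to-trial contrast. It does not recover a microdosing VAS for double failures.

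A reader might also infer more than the documents support:
- *That the trial VAS is undefined.* The visit is fixed by 1.8, 6.4.3 and 6.7. What is open is how scores on continuous mode are treated, and who is analysed.
- *That the microdosing VAS is certainly lost.* Source documents are to be kept (9.3) and the CRFs are held separately (Appendix D). Table 2 in 6.7 is not exhaustive: it also omits medication usage and the Programming Form. But 9.3 lets VAS go directly onto CRFs, so a separate source record is not assured.
- *That double failures are certainly scored on continuous mode.* The repeated step in 6.4.2 allows an End of Trial VAS before the switch, and Figure 1 is not available to settle the order. Section 6.4.3 favours the reading used here.
- *That everyone not on microdosing exits under 6.4.3.* That rule joins two conditions. The case for exit rests more on 1.8 and 6.4.2.
- *That the plan prescribes complete-row analysis.* It does not. That is one natural way to run the stated model, and the alternative has its own problem.
- *That every responder drops by at least 0.5 x 6.0 = 3.0 cm.* Sections 5.4.1 and 6.4.2 do not tie relief to the site that met 6.0 cm. Back 7.0 to 6.0 with leg 3.0 to 1.5 qualifies as worded, with drops of 1.0 and 1.5 cm.

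**Conclusion.** The point holds in limited form. The plan fixes the visit for the trial VAS, but not its treatment for subjects moved to continuous BurstDR, nor the subjects in the baseline-to-trial contrast. Neither natural way of running the stated analysis estimates the mean change on microdosing in all trialed subjects.

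The size cannot be taken from the documents, which give no failing share, no SD and no difference between modes. Under the assumed models the responders-only excess is roughly 0.3-0.4 cm if 10% fail and 0.5-1.4 cm if 20-40% fail; it tends to 0 as the failing share does. The mixed-mode shift is 0 on the plan's own premise, and 0.2-0.8 cm only if 20-40% switch and continuous mode adds 1-2 cm.

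The sponsor should make the change because it is cheap and an uncaptured score cannot be recovered. Confidence is medium, given the missing Figure 1 and the unseen CRFs.

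**What to change.** 1. Record the VAS already used at each in-trial reprogramming decision, with date and pattern in use, on the VAS or Programming Form, and add it to Table 2 in 6.7.
2. In Section 7, make baseline-to-trial change a paired analysis in all trialed subjects, using the last VAS on microdosing before any switch to continuous mode and the End of Trial VAS for everyone else. Report VAS and secondary scores taken on continuous mode separately.
3. Run the repeated measures ANOVA with Tukey comparisons over all visits in implanted subjects, and label it as applying to trial responders only.
4. Report the microdosing responder proportion out of all trialed subjects.

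The sponsor should also reconcile the 50% criterion in 6.4.2 with that in 6.4.3, the placement of the continuous-mode step within 6.4.2, and the stated trial length of around 3-7 days with the 7-9 days that the intervals imply. No clinical rule is proposed.

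Cost: one or two VAS entries per reprogrammed subject. If 20-40% of 60 fail both patterns (12-24 subjects), that is 2 x 12 = 24 to 2 x 24 = 48 entries, plus one for each subject who succeeds only on the second pattern; the ceiling is 2 x 60 = 120. No visit is added. Downsides: more data to monitor; an earlier reading for double failures (day 5-7 rather than day 7-9); still no secondary scores on microdosing for them; and a primary result split into two analyses.
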